#### ***9.1.1.4 Intensity of Adverse Events***

All AEs (or toxicities) including local injection site reactions encountered during the study will be evaluated according to the NCI CTCAE v4.0 [5] grading system (0 to 5), where applicable.

Grade	Description
1	Mild; asymptomatic or mild symptoms; clinical or diagnostic observations only; intervention not indicated.
2	Moderate; minimal, local or non-invasive intervention indicated; limiting age-appropriate instrumental activities of daily living.
3	Severe or medically significant but not immediately life-threatening; hospitalisation or prolongation of hospitalisation indicated; disabling limiting self care activities of daily living.

CONFIDENTIAL

Immudulon Therapeutics Ltd.  
[name]

- 4 Life-threatening consequences; urgent intervention indicated.
- 5 Death related to AE.

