##### Local and Systemic Toxicities

Local and systemic toxicities will be presented over the treatment period in standard frequency tables overall and by number, degree and type.

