2.2 Study Endpoint(s)

The Safety and Tolerability endpoints are:

- Local injection site tolerability
- Adverse Events with documentation of number, type and degree of toxicities as measured by the National Cancer Institute (NCI) Common Toxicity Criteria for Adverse Events (CTCAE) v4.0 [1] where appropriate.

The Efficacy endpoints are:

- Overall survival
- Reduction in metastatic disease.

Exploratory endpoints of change in markers of immune status are to be reported separately from the main endpoints of the study, and the analyses are not therefore described in this SAP.

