4. PLANNED ANALYSES

At the time of final analysis for the study, descriptive summaries of the results of the study will be provided along with data listings of the final study database. Summary statistics or frequency tables will be provided, where appropriate.

Section 9 provides details of the descriptive statistics and TFL shells are included in Section 13.

No formal statistical analyses of the results are anticipated and hence no statistical inferences will be made.

Planned analyses as detailed in the protocol are as follows:

The evaluation of safety and tolerability will be summarised using the Safety population and will be based on local and systemic toxicities (including injection site tolerability) which will be presented over the treatment period in standard frequency tables, overall and by number, degree and type. Adverse Events will

be presented descriptively to include related adverse events, serious adverse events (SAEs), and adverse events leading to withdrawal or death. The frequency and severity of injection site reactions, and all other safety parameters will be summarised.

All patients will have received IMM-101 in the context of both the Phase 1 study and, for the majority, on a Named Patient basis; therefore all AEs in this long term follow up study will be regarded as treatment emergent.

Efficacy will be presented using the Safety population and will be assessed through documenting the long-term clinical course of the patients previously enrolled in Study IMM-101-001 in terms of OS. Reduction in metastatic disease will be listed only.

Variables for the exploratory endpoints will be analysed and reported separately to the main efficacy and safety endpoints of the study.

The protocol specified that OS will be presented from enrolment into this study, in addition to time from initial diagnosis and enrolment into study IMM-101-001. Time zero for the OS analysis in this study (IMM-101-008) will be based on the date of Day 0 in this study and analysis of OS taking into account time from initial diagnosis and first dosing day in Study IMM-101-001 will not be included in this SAP as not all patients completing the FIH study entered the LTF study.

In addition to the above planned presentations, non-serious adverse events in LTF study patients will be tabulated and treatment-related treatment emergent AEs will also be presented combining data in these patients, from both the FIH and LTF studies.

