8. DATA HANDLING CONVENTIONS

8.1 Premature Withdrawal and Missing Data

Patients who withdraw early will be included in the analysis of safety and efficacy. Missing, unused and spurious data will be treated as such. No imputation methods will be applied, except for concomitant medication stop date as follows:

If the stop date for a medication is partially missing, it will be assumed to be a concomitant medication if, based on the partial information available, concomitant is not ruled out. Hence the date will be imputed to the end of the month/year, i.e. if day is unknown it will be set to the last day of the specified month, if day

and month are unknown it will be imputed as 31st December. This imputation will be also used in the determination of whether the previous medication was stopped within 14 days prior to Day 0.

Date imputations will not be shown in data listings however, the flag based on imputed dates will be shown in the listings. Date imputations will be incorporated into tabulations of previous/concomitant medications.

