- Treatment emergent, IMM-101-related, adverse events: AEs that are definitely, probably or possibly related to study drug or with an unknown relationship (Table 10d)
- Treatment emergent, SAEs (Table 10e)
- Treatment emergent adverse events leading to withdrawal or death (Table 10f).
- Treatment emergent non-serious adverse events (Table 10g).

Additionally, long term safety will be evaluated by combining treatment related adverse event experience in the FIH study through to the end of the LTF study by summarising treatment emergent treatment-related adverse events (IMM-101-001 and IMM-101-008 Combined) (Table 10h).

Where it is not applicable to grade an AE using NCI CTCAE grade, it will be excluded from the summary of NCI Grade 3 and above AEs. Any AEs with missing grades, however, will be included, based on a worst-case approach.

On-study injection site reactions are summarised over the treatment period by visit in Table 11.

Urine Pregnancy Test Results and blood samples for immunological markers will be listed but not summarised.

All safety data will be listed.

Any comments recorded as free text in the CRF will be listed.

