Note to programmer: Decimal places for continuous data summaries are based on the variable recorded in the data being to zero decimal places. If the decimal places recorded are increased in the data then increase decimal places for mean, median, SD, min and max in the table accordingly.

CONFIDENTIAL**Exploristics Limited**

Identifier: EXP12002

Clinical Study Identifier: IMM-101-008

Final Analysis

Protocol: IMM-101-008

Analysis Population: Safety Population

Page x of y

Table 9b
Time on IMM-101 Treatment (IMM-101-001 and IMM-101-008 Combined)

Overall study drug exposure (months)

N	X
Mean	xx.xx
Std	xx.xxxx
Median	xx.xx
Min.	xx.x
Max.	xx.x

Note: Overall study drug exposure is derived as follows:

Overall study drug exposure (months) = (date of last dose in study IMM-101-008 - date of first dose in study IMM-101-001 + 1) / 30.4375.

Code: S:\Services\Immodulon\IMM-101-008\Analysis\Development\Code\ Table9b.sas ddmmmyy:hh:mm:ss

Data: S:\Services\Immodulon\IMM-101-001\RawData_SDSTM\xxxxxx.sas7bdat,

S:\Services\Immodulon\IMM-101-001\RawData_SDSTM\xxxxxx.sas7bdat,

S:\Services\Immodulon\IMM-101-008\SDTM\xxxxxx.sas7bdat

Note to programmer: Please update data footnote with appropriate file directory.

CONFIDENTIAL**Exploristics Limited**

Identifier: EXP12002

Clinical Study Identifier: IMM-101-008

Final Analysis

Protocol: IMM-101-008

Analysis Population: Safety Population

Page x of y

Table 10a
Summary of Treatment Emergent Adverse Events

	N = xx (%)
Number of patients with treatment emergent adverse events (%)	xx (xx.x)
Number of treatment emergent adverse events	xx
Number of patients with treatment emergent adverse events related to the study drug (%)	xx (xx.x)
Number of treatment emergent adverse events related to the study drug	xx
Number of patients with serious treatment emergent adverse events (%)	xx (xx.x)
Number of serious treatment emergent adverse events	xx
Number of patients with serious treatment emergent adverse events relating to the study drug (%)	xx (xx.x)
Number of serious treatment emergent adverse events relating to the study drug	xx
Number of patients with treatment emergent adverse events leading to withdrawal or death (%)	xx (xx.x)
Number of treatment emergent adverse events leading to withdrawal or death	xx
Number of patients with treatment emergent adverse events of NCI CTCAE \geq Grade 3 (%)	xx (xx.x)
Number of treatment emergent adverse events of NCI CTCAE \geq Grade 3	xx

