Unique Patient ID	AE No.	Reported AE term	Preferred Term	System Organ Class	Intensity (CTCAE)	Seriousness (N/Y)	Reason for Seriousness/ Details if other	Relationship to Study Drug	Start Date/Time (DD-MM-YYYY HH:MM)	End Date/Time (DD-MM-YYYY HH:MM)	Outcome	Sequelae
xxxxx	xx	xxxxx	xxxxx	xxxxx	xxxxx	xx	xxxxx	xxxxx	DD-MM-YYYY HH:MM	DD-MM-YYYY HH:MM	xxxxx	xxxxx
xxxxx	xx	xxxxx	xxxxx	xxxxx	xxxxx	xx	xxxxx	xxxxx	DD-MM-YYYY HH:MM	DD-MM-YYYY HH:MM	xxxxx	xxxxx
xxxxx	xx	xxxxx	xxxxx	xxxxx	xxxxx	xx	xxxxx	xxxxx	DD-MM-YYYY HH:MM	DD-MM-YYYY HH:MM	xxxxx	xxxxx
xxxxx	xx	xxxxx	xxxxx	xxxxx	xxxxx	xx	xxxxx	xxxxx	DD-MM-YYYY HH:MM	DD-MM-YYYY HH:MM	xxxxx	xxxxx
xxxxx	xx	xxxxx	xxxxx	xxxxx	xxxxx	xx	xxxxx	xxxxx	DD-MM-YYYY HH:MM	DD-MM-YYYY HH:MM	xxxxx	xxxxx
xxxxx	xx	xxxxx	xxxxx	xxxxx	xxxxx	xx	xxxxx	xxxxx	DD-MM-YYYY HH:MM	DD-MM-YYYY HH:MM	xxxxx	xxxxx
xxxxx	xx	xxxxx	xxxxx	xxxxx	xxxxx	xx	xxxxx	xxxxx	DD-MM-YYYY HH:MM	DD-MM-YYYY HH:MM	xxxxx	xxxxx
xxxxx	xx	xxxxx	xxxxx	xxxxx	xxxxx	xx	xxxxx	xxxxx	DD-MM-YYYY HH:MM	DD-MM-YYYY HH:MM	xxxxx	xxxxx

Note: Treatment emergent AEs are all those reported during the study. Sequelae column also contains comments recorded in the sequelae field of the CRF.

Note: Preferred Term and System Organ Class are coded using MedDRA version x.xx.

Note: Common Toxicity Criteria for Adverse Events CTCAE code. 1. Mild, 2. Moderate, 3. Severe, 4. Life Threatening, 5. Death

Code: S:\Services\Immodulon\IMM-101-008\Analysis\Development\Code\Listing12.sas ddmmmyy:hh:mm:ss

Data: S:\Services\Immodulon\IMM-101-008\xxxx.sas7bdat

Note to programmer: Please update data footnote with appropriate file directory.

Note to Programmer: Where applicable, separate date from time using a space.

Note to Programmer: If Reason for seriousness is other please include reason/description.

Note to Programmer: Intensity should be occupied with text, the numeric CTCAE codes are provided in a note.

Note to programmer: Please add relevant version number in MedDRA note to reflect version used at time of coding.

Note to programmer: If necessary, break table over two pages with each new section of the table displaying Unique Patient ID, AE No., Reported AE term, Preferred Term and System Organ Class.

CONFIDENTIAL

Exploristics Limited

Identifier: EXP12002

Clinical Study Identifier: IMM-101-008

Final Analysis

Protocol: IMM-101-008

Page x of y

Analysis Population: Safety Population

Listing 13
On-Study Injection Site Reaction(s)

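### AE tables show CTCAE degree only as a single Grade 3 or higher cut, and missing grades are counted in that cut without being shown

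*SAP*

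**What the plan says.** Protocol 10.1.1.1, under Local and Systemic Toxicities, states: "Local and systemic toxicities will be presented over the treatment period in standard frequency tables overall and by number, degree and type". SAP section 4 repeats this as a planned analysis, with "standard frequency tables, overall and by number, degree and type". SAP 2.2 defines the endpoint as "Adverse Events with documentation of number, type and degree of toxicities", measured by CTCAE v4.0 where appropriate.

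SAP 9.3 and the shells in SAP 13.2 deliver the following:

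- **Table 10a** has two rows on grade, one for patients and one for events. The patient row opens "Number of patients with treatment emergent adverse events of NCI CTCAE" and continues with the Grade 3 or higher condition.
- **Table 10c** gives the Grade 3 or higher AEs by system organ class (SOC) and preferred term (PT).
- **Tables 10b and 10d to 10h** have no grade breakdown. Tables 10d and 10h are the tables of related AEs.
- **Listing 12** shows each AE's grade. Its programmer note reads: "Intensity should be occupied with text, the numeric CTCAE codes are provided in a note".

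For the Grade 3 or higher summary, SAP 9.3 leaves out AEs that cannot be graded, but of missing grades it says: "Any AEs with missing grades, however, will be included, based on a worst-case approach". SAP 8.1 says: "No imputation methods will be applied, except for concomitant medication stop date as follows".

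Two further rules matter. Protocol 9.4 requires a change in an AE's severity to be entered as a separate event, and the Table 10 notes define m as the total of events recorded. Protocol 9.1.1.4 extends grading to local reactions: "All AEs (or toxicities) including local injection site reactions encountered during the study will be evaluated according to the NCI CTCAE v4.0", where applicable.

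**The concern.** Safety and tolerability is the primary objective (protocol 9.1), and degree is one of the three things by which AEs are to be documented. A single cut at Grade 3 shows little of a five-grade scale. Grades 1 and 2 are never separated, Grades 3, 4 and 5 are merged, and related AEs have no grade in any table. For a long-term study of a product whose expected reactions are mild to moderate, most of the information is likely to lie below the cut.

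The missing-grade rule makes the one available cut harder to read. An AE observed at Grade 3 and an AE with no recorded grade fall in the same cell, and nothing in Table 10a or 10c tells the reader so. In a cohort this small, one such patient visibly changes the percentage.

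**Working it through.** The plan states no figure on this point (protocol 10.2 and 10.3 are marked not applicable), so there is nothing to reproduce.

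**1. Grade information that the tables yield.** In Table 10b, n counts each patient with at least one AE once. In Table 10c, n counts each patient with at least one AE of Grade 3 or higher or of missing grade. The difference is the number of patients whose AEs were all Grade 1, Grade 2 or not gradable. Grade 1 cannot be separated from Grade 2, nor Grade 3 from 4 or 5. For related AEs even this subtraction is unavailable, because Table 10d has no Grade 3 or higher counterpart.

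**2. Effect of a missing grade.** A patient with a missing-grade AE and no observed Grade 3 or higher AE enters the numerator only through the worst-case rule, and adds 100/N percentage points. N is not given, so I assume a range:

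- N = 10, from the 2x5 panel layout in the Figure 1a shell (weak evidence)
- N = 12, from protocol 4.2: 18 eligible patients less 3 + 1 + 2 who had stopped by August 2011
- N = 19, all patients enrolled in Phase 1 (protocol 3.3), as an upper limit

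| Assumed N | One such patient (points) | Two such patients (points) |
|---|---|---|
| 10 | 100/10 = 10.0 | 200/10 = 20.0 |
| 12 | 100/12 = 8.3 | 200/12 = 16.7 |
| 19 | 100/19 = 5.3 | 200/19 = 10.5 |

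For example, at N = 10 with one observed Grade 3 patient and one missing-grade patient, Table 10a would show 2/10 = 20.0%, where the observed figure is 1/10 = 10.0%. With missing grades in their own row, the observed figure does not move. The number of such patients is unknown and may be zero.

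**3. SAP 8.1 against SAP 9.3.** Section 8.1 allows one exception to no imputation, the stop date of a medication. Treating a missing grade as Grade 3 or higher is a second exception that section 8.1 does not list.

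**4. What m counts.** Take one AE graded 2, then 3, then 2, recorded as protocol 9.4 requires. It gives three records, so n = 1 and m = 3 in Table 10b. One record is Grade 3, so m = 1 in Table 10c. The difference in m is 3 - 1 = 2 records below Grade 3, from an AE whose worst grade was 3. This only illustrates the rule; n and its percentage are unaffected.

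**The case against.** The strongest reply is that the plan does present degree. Neither document defines degree as a split by every grade, the endpoint is qualified by where appropriate, and the detailed AE list in protocol 10.1.1.1 asks for no grade breakdown, so Table 10c goes beyond that list. Every grade is in Listing 12. This stands to the extent that a reader should not infer a breach of the protocol or a loss of data: the gap is in the summary tables. It does not remove the point, because degree is named in both the planned tables and the endpoint, and one cut with none for related AEs is a thin summary of it.

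The missing-grade rule is pre-specified, explicit and conservative: it can only raise reported severity. Protocol 9.4 also requires a grade for each AE, so missing grades may not occur. That is accepted. The rule itself can stay; what is lacking is disclosure in the tables and a cross-reference in SAP 8.1.

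Two stronger readings are not supported:

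- **That m is wrong.** Protocol 9.4 makes a severity change a separate event, and the table notes count events recorded, so the two agree. The notes only fail to warn that one continuing AE may contribute several records. The AE CRF is not among the documents, so the size of any difference from an episode count is unknown. Rebuilding episodes from dates would need judgement that the listed fields do not clearly support.
- **That the severity of local reactions is not summarised.** Table 11 tabulates the five-level effect on daily activities by visit, with worsening and wound care. This partly meets protocol 9.1.3.1 and the requirement in protocol 10.1.1.2 to summarise severity. What remains open is whether a CTCAE grade was collected for reactions not recorded as AEs, since protocol 9.2 leaves that recording to the Investigator.

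**Conclusion.** The point holds for the summary tables. CTCAE degree, part of the AE endpoint, is tabulated only as Grade 3 or higher. No table grades related AEs, and missing grades are merged into the one cut without a footnote or a row of their own. Each patient counted only because of a missing grade moves the Grade 3 or higher percentage by 8.3 to 10.0 points at an assumed N of 12 to 10, or 5.3 points at N = 19. Both N and the number of such patients are unknown, and the latter may be zero. The study is descriptive, so no inference is affected. The change is still worth making, because it alters what the primary safety summary can show. The m point warrants a footnote only, and the local-reaction point a statement in the report.

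**What to change.** In the SAP:

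1. Add a table of patients by worst CTCAE grade (1, 2, 3, 4, 5, not gradable, missing), overall and by SOC and PT, for all AEs and for related AEs.
2. In Tables 10a and 10c, show observed Grade 3 or higher separately from missing grade, keep the pre-specified worst-case count as a second row, and list the rule as an exception in SAP 8.1.
3. Footnote Tables 10a to 10g: m counts AE records, and under protocol 9.4 an AE that changes severity contributes more than one; n and percentages are unaffected. Do not reconstruct episodes from dates. The footnote stops short of Table 10h because the documents do not give the recording rule for its Phase 1 part.

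A minor addition for the report: state whether a CTCAE grade was collected for local reactions not recorded as AEs, and show it if so.

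The AE changes use fields already in Listing 12 (coded terms, intensity, relationship), with no new data collection. The cost is SAP wording, extra rows, footnotes and one more table, whose cells will be small in a cohort of this size.
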